8.2.1 REPEATED AND SERIOUS NON-COMPLIANCE

In the event of repeated non-compliance or one-time serious non-compliance (as determined by the Sponsor), a Clinical Research Associate or clinical representative will attempt to secure compliance by one or more of the following actions:

- Visiting the investigator
 - Contacting the investigator by telephone
 - Contacting the investigator in writing
- Retraining of the investigator and/or site personnel
 - Corrective and Preventive Action (CAPA)

If an investigator is found to be repeatedly non-compliant with the CIP, research contract, or any other conditions of the study, the Sponsor will either secure compliance or, at its sole discretion, suspend or terminate the investigator's participation in the clinical study.

9 DATA MANAGEMENT

Overall, the Sponsor will be responsible for the data handling. The Sponsor and/or its affiliates will be responsible for compiling and submitting all required reports to governmental agencies.

Data will be analyzed by the Sponsor and may be transferred to the Sponsor's locations or regulatory authorities worldwide in support of a market-approval application.

Clinical Investigational Plan

The PI or institution will provide direct access to source data during and after the clinical study for monitoring, audits, IRB review and regulatory authority inspections. As required, the PI or institution will obtain permission for direct access to source documents from the subject, hospital administration, and national regulatory authorities before starting the clinical study.

9.1 DATA MANAGEMENT PLAN

A detailed Data Management Plan (DMP) will be established to ensure consistency of the data. This document will include procedures used for data review, database cleaning, and the issuance and resolution of data queries. If appropriate, the DMP may be updated throughout the study. All revisions will be tracked and document controlled.

CRF data will be captured in a validated electronic database management system hosted by the Sponsor. Only specially trained designated site personnel will be permitted to enter the CRF data through the EDC system. An electronic audit trail will be used to track any subsequent changes of the entered data.

9.2 DOCUMENT AND DATA CONTROL

9.2.1 TRACEABILITY OF DOCUMENTS AND DATA

The PI will ensure accuracy, completeness, legibility, and timeliness of the data reported to the Sponsor on the CRFs and in all required reports.

9.2.2 RECORDING DATA

Original documentation supporting the data recorded in the CRFs must be maintained, including clinical charts, medical records, laboratory reports, physician referral or consultation letters, X-ray reports, etc. AEs, which are managed at a health care facility other than the study site, must be reported to the Sponsor and every attempt must be made to obtain source documentation from that facility.

The EDC CRFs will be electronically validated by the designated site personnel. Any change or correction to data will be recorded in the EDC system's audit trail.

10 MONITORING

It is the responsibility of the Sponsor to ensure that the study is conducted, recorded, and reported in accordance with the approved CIP, subsequent amendment(s), applicable regulations, and guidance documents.

Prior to beginning the study, the Sponsor will contact the PI and designated site personnel to discuss the study and data requirements.

Centralized monitoring will occur through routine internal data review. This monitoring is designed to identify missing and inconsistent data, data outliers, and potential CIP deviations that may be indicative of site non-compliance. Remote monitoring will be performed. On-site monitoring may occur in lieu of remote monitoring at the discretion of the sponsor. A Sponsor monitor may periodically review the subject records and associated source documents. The PI will make subject and study records available to the clinical monitor for monitoring.

Clinical Investigational Plan**11 REGULATORY INSPECTIONS**

The PI or designated site personnel should contact the Sponsor immediately upon notification of a governmental agency inspection at the site. A clinical monitor or designee will assist the site in preparing for the audit.

An investigator who has authority to grant access, will permit authorized governmental agency employees, at reasonable times and in reasonable manner, to enter and inspect any establishment where devices are held (including any establishment where devices are used or where records or results are kept).

An investigator, or designated site personnel, will permit authorized governmental agency employees, at reasonable times and in reasonable manner, to inspect and copy all records relating to the study.

An investigator will permit authorized governmental agency employees to inspect and copy records that identify subjects, upon notice that governmental agency has reason to suspect that adequate informed consent was not obtained, or that reports required to be submitted by the investigator, to the Sponsor or IRB have not been submitted or are incomplete, inaccurate, false, or misleading.

12 STATISTICAL CONSIDERATIONS

PREVENT II is a prospective, multi-center, randomized, double-blinded, placebo-controlled study evaluating the risk of subjects over 50 years of age being managed on warfarin therapy alone compared to warfarin and ASA therapy together. The two groups in the study are as follows:

- 1) Treatment Arm: Warfarin (INR target: 2.0-2.5, median: 2.25) + Placebo (1 pill/day)
- 2) Control Arm: Warfarin (INR target: 2.0-2.5, median: 2.25) + ASA therapy (81mg/day)

In general, continuous data will be presented as the number of subjects, mean with standard deviation, median, minimum, and maximum values. Categorical data will be reported as frequencies and percentages. Adverse events will additionally be reported as events per subject year, with only those events that start after implantation of the HM II analyzed. The adverse events will be compared between the two arms of the study using risk ratios (Poisson's regression). Survival data will be presented and analyzed using the Kaplan-Meier method.

The primary endpoints will be analyzed per protocol method as defined in **Section 12.1**. Every effort will be made to avoid crossovers, but in such instances, analysis will be performed in accordance with **Section 12.1**. The study will be conducted in a double-blinded fashion with neither the investigator, nor the subject having the knowledge of whether the subject is in the Treatment or the Control Arm. Only the primary statistician from the Sponsor will have knowledge of the specific groups, and all other parties will be blinded.

Every effort will be made to collect all required data. A one-sided 0.025 level of significance or two-sided 0.05 level of significance will be used to declare statistical significance as outlined below. Multiplicity adjustments will not be made unless specified below. A sensitivity analysis will be performed to account for any bias that may have been introduced by subjects withdrawing from the study or being removed from the study.

Clinical Investigational Plan**12.1 STATISTICAL DESIGN, HYPOTHESES, METHOD AND ANALYTICAL PROCEDURES**

Subjects will be block randomized per site on a 1:1 ratio into the Treatment and Control Arms. The study is designed to satisfy two primary endpoints. Both primary endpoints must be met for the study to be successful.

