4.5 ENDPOINTS**4.5.1 PRIMARY ENDPOINTS**

There are two primary endpoints of this study:

Efficacy Endpoint (Superiority): Composite incidence of non-surgical bleeding at 6 months post initial implantation, including but not limited to GI, GU, epistaxis, subdural hematoma, and primary hemorrhagic stroke (not due to ischemic conversion, or due to the treatment of a hemolysis/suspected thrombosis event).

Safety Endpoint (Non-Inferiority): Composite incidence of pump thrombosis and TE stroke at 6 months post initial implantation, including ischemic stroke, or hemorrhagic stroke due to an ischemic conversion/treatment of hemolysis/pump thrombosis event.

Clinical Investigational Plan**4.5.2 DESCRIPTIVE ENDPOINTS**

The descriptive endpoints will involve a comparison between the Treatment and Control Arms in the rates of:

- Overall bleeding
- GI bleeding
- Suspected and confirmed pump thrombosis
- Stroke (both ischemic and hemorrhagic)
- Hemolysis (major and minor)
- As treated analysis of anticoagulation and antiplatelet medications
- Survival
- Assessment of adherence to the PREVENT study recommended practices.

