12.1.3 SAMPLE SIZE

A total sample size of up to 350 subjects will provide adequate power to satisfy both the primary efficacy and the safety endpoints respectively. The assumptions and rationale are provided in the sections below.

Clinical Investigational Plan**12.1.4 PRIMARY EFFICACY ENDPOINT**

Assumptions: Based on the analysis of the first 100 subjects enrolled in the PREVENT study (Data on file), the anticipated incidence of non-surgical bleeding in the Control Arm at 6 months is 40%. The assumption for PREVENT II is that there will at least be a 15% reduction in the incidence of non-surgical bleeding in the Treatment Arm compared to the Control Arm.

The comparison of Treatment and Control Arms will be made using the Fishers Exact Test. The primary endpoint for efficacy will be considered to be met if the p -value ≤ 0.05 . A sample size of 330 subjects (165 in each of the Treatment and Control Arms) with an alpha of 0.05 will provide 80% power to demonstrate a significant difference between the Treatment and Control Arms.

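### The Poisson comparison of adverse events makes no provision for overdispersion or repeat events, so intervals for bleeding rate ratios are likely to be too narrow if bleeding risk differs between subjects

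*Combined protocol and SAP*

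**What the plan says.** Section 12 (Statistical Considerations) first gives frequencies and percentages for categorical data. It then says "Adverse events will additionally be reported as events per subject year", and continues: "The adverse events will be compared between the two arms of the study using risk ratios", with Poisson regression named in parentheses. Nothing in Section 12 or elsewhere mentions overdispersion, a negative binomial model, a robust or clustered variance, a subject random effect, an offset, or how repeat events in one subject are counted.

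Section 4.5.2 lists the outcomes to which this matters: "The descriptive endpoints will involve a comparison between the Treatment and Control Arms in the rates of" overall bleeding, GI bleeding, pump thrombosis, stroke and hemolysis, among others. The Synopsis says the descriptive endpoints are evaluated at 12 months. On multiplicity, Section 12 says: "Multiplicity adjustments will not be made unless specified below".

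The two primary endpoints use other methods. Sections 12.1.1 and 12.1.2 count each subject once. Section 12.1.4 uses Fisher's exact test and Section 12.1.5 a confidence limit for the risk difference.

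**The concern.** Events per subject-year count every event, and Section 6.7.3 ends follow-up early only for death, transplant, explant or withdrawal. A subject who bleeds therefore normally stays in the study and can contribute further bleeds.

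Poisson regression with its default variance takes the variance of each subject's count to equal its mean. That holds if all subjects in an arm share one rate. It fails if some subjects are more prone to bleed than others, because a few subjects then supply many of the events and the data carry less information than the event total suggests.

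The documents give reason to expect such differences. Section 2.3 says older patients have a higher bleeding risk, and Table 2 collects prior bleeding history (arteriovenous malformations, ulcers, diverticular disease, anemia).

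What is at stake is the coverage of the 12-month bleeding comparisons. Too narrow an interval would make a chance difference between arms look established.

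**Working it through.** **Inputs from the plan.** 175 subjects per arm and at most 12 months of follow-up (Synopsis); control-arm bleeding, "the anticipated incidence of non-surgical bleeding in the Control Arm at 6 months is 40" per cent (Section 12.1.4); control-arm thromboembolic incidence of 8% at 6 months (Section 12.1.5); two-sided level 0.05 (Section 12).

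**Inputs assumed.** The documents give no recurrence rate, dispersion or dropout rate. The frailty variance k is therefore varied from 0 to 2. Exits are exponential at 0.25 per year, so 1 − exp(−0.25) = 22% leave by one year.

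**The plan's own figures.** None is given for the Poisson comparison, so the anchors were checked instead.
- Efficacy: 40% against 25% (the 15% taken as percentage points) with continuity correction gives 165 per arm, as stated. Exact Fisher power at 165 is 80.5%.
- Safety: Farrington-Manning with 8% against 9%, margin 10 points and one-sided 0.025 gives 168.6, so 169 per arm, as stated. Power is 80.1%.

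**Counts of bleeds.** Let a subject's count be Poisson given a gamma frailty with mean 1 and variance k.
- Setting the chance of no bleed by 6 months to 0.60 gives a 6-month mean m6 = (0.60^(−k) − 1)/k, or −ln 0.60 = 0.511 when k = 0.
- Over 12 months m12 = 2 × m6, and the variance is φ = 1 + k × m12 times the Poisson variance.
- With no true arm difference, model-based type I error is 2[1 − Φ(1.96/√φ)].

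Example, k = 1: m6 = 1/0.60 − 1 = 0.667; m12 = 1.333; φ = 2.33; √φ = 1.53; type I error = 19.9%.

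A simulation of 20,000 trials per case, with the assumed exits, checked this and added a subject-level robust variance:

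| k | m12 | φ | Formula | Simulated, model-based | Simulated, robust | Robust SE / model-based SE |
|---|---|---|---|---|---|---|
| 0 | 1.02 | 1.00 | 5.0% | 4.8% | 5.0% | 1.00 |
| 0.25 | 1.09 | 1.27 | 8.2% | 7.5% | 4.9% | 1.12 |
| 0.5 | 1.16 | 1.58 | 11.9% | 11.4% | 5.1% | 1.24 |
| 1 | 1.33 | 2.33 | 19.9% | 19.4% | 5.4% | 1.49 |
| 2 | 1.78 | 4.56 | 35.8% | 35.2% | 5.4% | 2.07 |

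The formula runs slightly above the simulation because it assumes that everyone completes 12 months. The row k = 0 still has about one bleed per subject-year, with repeats, and shows no inflation.

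**Rarer events.** Replacing 0.60 by 0.92 (8% at 6 months), the formula over 12 months gives φ = 1.17 and 7.0% at k = 1, and φ = 1.36 and 9.3% at k = 2.

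**One yes/no result per subject.** Model-based Poisson takes the variance of the log risk ratio as 1/y1 + 1/y2, where y1 and y2 are the numbers of subjects with an event. The correct variance subtracts 1/n for each arm. At 40% incidence the true variance is 1 − 0.40 = 0.60 of the assumed one. Type I error is 2[1 − Φ(1.96/√0.60)] = about 1.1%, and 1.05% in simulation. The corrected variance gave 4.6%.

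**The case against.** The strongest reply has four parts.

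**Nothing decisive rests on it.** This stands. Study success depends only on the two primary endpoints, and neither uses this model. The significance levels in Section 12 are applied as set out further on in that section, and only the two primary tests are set out there. The listed outcomes are called descriptive and carry no hypotheses. A reader might infer that the Steering Committee's safety reviews are affected, but Section 12.3 does not say which method they use.

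**Repeat events alone are harmless.** This also stands. A reader might infer that recurrence by itself makes the intervals too narrow, but at a common rate the test holds its level (4.8%). Subjects must differ in risk, or one event must alter the chance of the next. The documents support differing risk only qualitatively.

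**The plan does not state a wrong variance.** This is correct. Section 12 names Poisson regression and no variance estimator, so a robust variance is not excluded. The gap is one of specification.

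**The target may be a risk ratio.** Percentages are reported too, and a reader who treats the term as a slip for rate ratio goes beyond the text. Under the yes/no reading the intervals are too wide, not too narrow. This removes certainty about the direction of the error but does not rescue the sentence: the default variance is wrong for a yes/no result and, when risks differ, for counts. A robust variance serves both.

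**Conclusion.** The point holds as a conditional one. If event counts are compared with the default Poisson variance and bleeding risk differs between subjects, intervals for bleeding rate ratios are likely to be too narrow. For assumed frailty variances from 0.25 to 2, two-sided type I error runs from about 7.5% to 35%, and correct intervals would be about 1.1 to 2.1 times as wide on the log scale. The 40% bleeding anchor is the plan's; the frailty variances and exit rate are not.

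It would be tempting to extend these figures to stroke and pump thrombosis. At the plan's 8% composite incidence the inflation is only to about 7% to 9% at frailty variance 1 to 2, so this is mainly a point about bleeding.

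**What to change.** Replace the sentence in Section 12 with one to this effect: event rates, counting all events including repeats, will be compared between arms as rate ratios with 95% confidence intervals by negative binomial regression, or by Poisson regression with robust variance clustered on subject, with log follow-up time as offset. If subject-level risk ratios are also reported, use Poisson regression with robust variance, and label the two measures separately.

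The cost is a sentence in the plan and a model option in the program. No extra data or subjects are needed. The downside is wider intervals where events cluster within subjects.

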12.1.1 PRIMARY EFFICACY ENDPOINT

The primary efficacy endpoint is the incidence of non-surgical bleeding within the first 6 months of support. If a subject experiences any non-surgical bleeding including GI bleeding, epistaxis, subdural hematoma, or a primary hemorrhagic stroke (not due to an ischemic conversion or due to a treatment of a hemolysis/suspected thrombosis event), then the subject will be counted as having reached the primary efficacy endpoint. The determination of whether a hemorrhagic stroke is due to ischemic conversion or due to treatment of a hemolysis/suspected thrombosis event or is a primary hemorrhagic stroke will be made by the Clinical Events Committee (CEC).

The incidence of non-surgical bleeding will be compared between the Treatment and Control Arms using the following null and alternative hypotheses as follows:

$$H_0: \pi_{\text{TREATMENT}} \geq \pi_{\text{CONTROL}}$$

$$H_A: \pi_{\text{TREATMENT}} < \pi_{\text{CONTROL}}$$

where $\pi_{\text{TREATMENT}}$ and π_{CONTROL} are the incidence rates of non-surgical bleeding in the Treatment and Control Arms, respectively.

12.1.2 PRIMARY SAFETY ENDPOINT

The primary safety endpoint is the composite incidence of TE events within the first 6 months of HM II support. If a subject experiences any TE event, including pump thrombosis, ischemic stroke, or hemorrhagic stroke as a result of treatment of a suspected thrombosis/hemolysis event, then the subject will be counted as having reached the primary safety endpoint. The determination of whether a hemorrhagic stroke is due to ischemic conversion or due to treatment of a hemolysis/suspected thrombosis event or is a primary hemorrhagic stroke will be made by the Clinical Events Committee (CEC).

The incidence of TE events in the Treatment Arm will be compared to the Control Arm in a non-inferiority manner. The null and alternative hypotheses are as follows:

$$H_0: \pi_{\text{TREATMENT}} \leq \pi_{\text{CONTROL}} + \Delta$$

$$H_A: \pi_{\text{TREATMENT}} > \pi_{\text{CONTROL}} + \Delta$$

where $\pi_{\text{TREATMENT}}$ and π_{CONTROL} are the incidence rates of TE events in the Treatment and Control Arms respectively, and where Δ is the non-inferiority margin.

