Maximum follow-up duration per subject will be 12 months. Primary endpoints will be evaluated at 6 months. Individual components of the primary endpoints along with the descriptive endpoints will be evaluated at 12 months.

Clinical Investigational Plan

Study Synopsis

Statistical Considerations	
Primary Efficacy Endpoint Analysis – Reduction of Bleeding: The rate of non-surgical bleeding at 6 months will be compared between the Treatment and Control Arms utilizing the Fisher’s Exact Test. The primary endpoint for efficacy will be assumed to be met if the p-value < 0.05. The assumption is that there will be a 15% rate reduction at 6 months.
 
A sample size of 330 subjects (165 in each arm) with an alpha of 0.05 will provide 80% power to demonstrate a significant difference between the Treatment and Control Arms.
 
Primary Safety Endpoint Analysis – Non-Inferiority of Stroke and Thrombus: The difference in the rates of the composite endpoint of stroke and pump thrombosis between Treatment and Control Arms and the 95% confidence limit of the difference will be evaluated. If the upper confidence limit of the difference is < 10% then the non-inferiority criterion will be considered to have been met.
 
A sample size of 338 subjects (169 in each arm) will provide 80% power, with a target alpha of 0.025 (because this will be a one-sided test on the upper confidence limit) to demonstrate non-inferiority of the Treatment Arm to the Control Arm.
 
A total study sample size of 350 subjects will provide enough statistical power to demonstrate both efficacy and safety of the warfarin only anticoagulation regimen in these patients.
 
Both primary endpoints must be met for the study to be successful.
 
Intermediate Safety Assessment: A safety assessment will be performed after 60 subjects have completed 3 months of follow-up. Both incidence of stroke and pump thrombosis will be analyzed and results will be presented to the Steering Committee. Additionally, after the initial 3-month safety review, an analysis of AEs associated with primary endpoints will be presented to the Steering Committee for continued safety assessment in regular 6-month intervals. The Steering Committee will review the findings and make a decision to proceed or stop the study due to safety concerns.

Devices Used	HM II Left Ventricular Assist Device (LVAD)

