12.1.5 PRIMARY SAFETY ENDPOINT

Assumptions: Based on the analysis of the first 100 subjects enrolled in the PREVENT study (Data on file), the anticipated composite incidence of TE events in the Control Arm at 6 months is expected to be 8%. The assumption for PREVENT II is that the Treatment Arm will experience an incidence of TE events of no more than 9% at 6 months. The Treatment Arm will be considered non-inferior to the Control Arm if the upper one-sided 95% confidence limit of the risk difference in the 6 month TE rate between research drug arms (Treatment - Control) is less than +10% ("positive 10%", where 10% is the non-inferiority Δ in the above null and alternative hypotheses).

A sample size of 338 subjects (169 each in the Treatment and Control Arms) will achieve 80% power to prove the Treatment Arm is non-inferior to HM II when the margin of non-inferiority is 10% ($=\Delta$ in the above null and alternative hypotheses) using the Farrington-Manning risk difference approach to non-inferiority at a one-sided alpha = 0.025.

[figure not shown]

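### Section 12.1.2 states the safety hypotheses in the reverse direction from the non-inferiority rule and sample size, and Section 12.1.5 sets the confidence limit at a different alpha from the rest of the plan

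*Combined protocol and SAP*

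**What the plan says.** Section 12.1.2 introduces the primary safety comparison with "The incidence of TE events in the Treatment Arm will be compared to the Control Arm in a non-inferiority manner". The hypotheses printed beneath it, with the margin written as Δ, are:

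- null: "H_0: \pi_{\text{TREATMENT}} \leq \pi_{\text{CONTROL}} + \Delta"
- alternative: "H_A: \pi_{\text{TREATMENT}} > \pi_{\text{CONTROL}} + \Delta"

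The success rule appears twice. The synopsis says "If the upper confidence limit of the difference is < 10% then the non-inferiority criterion will be considered to have been met". Section 12.1.5 has the Treatment Arm "considered non-inferior to the Control Arm if the upper one-sided 95% confidence limit of the risk difference" (Treatment minus Control) is under +10%, and identifies that 10% as the Δ of the hypotheses above it. The same section says 169 subjects per arm "will achieve 80% power to prove the Treatment Arm is non-inferior to HM II when the margin of non-inferiority is 10"%, by the Farrington-Manning method at one-sided alpha 0.025.

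On the error rate, the synopsis sizes the safety endpoint "with a target alpha of 0.025 (because this will be a one-sided test on the upper confidence limit"), and the opening of Section 12 says "A one-sided 0.025 level of significance or two-sided 0.05 level of significance will be used to declare statistical significance". Both primary endpoints must be met for the study to succeed.

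**The concern.** A higher thromboembolic rate is worse. In a non-inferiority test, the claim to be proved (excess below the margin) belongs in the alternative, and unacceptable excess belongs in the null. Section 12.1.2 has them the other way round, although the efficacy hypotheses in Section 12.1.1 are printed correctly, with the desired conclusion in the alternative. Section 12.1.5 refers back to the Section 12.1.2 hypotheses when it defines the margin, so the plan ties its success rule and its power statement to a pair that contradicts both.

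The second inconsistency concerns the level. An upper one-sided 95% limit is a test at one-sided alpha 0.05. The sample size in the same section, the synopsis and Section 12 all use 0.025. Anyone who corrects Section 12.1.2 and states the alpha there will find that it disagrees with the limit in Section 12.1.5.

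At stake is the formal definition of one of two co-primary endpoints, the one that guards against the harm acknowledged in Section 3. A p-value programmed from the printed pair would test the wrong claim, and the choice between the two confidence levels can change the verdict.

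**Working it through.** **Inputs** (Section 12.1.5 unless stated): π_T = 0.09, π_C = 0.08, Δ = 0.10, one-sided alpha 0.025, power 80%, 1:1 allocation, Farrington-Manning score test. Planned enrolment is 175 per arm (synopsis).

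**1. Reproduce the plan's sample size in the non-inferiority direction** (H0: π_T ≥ π_C + Δ).

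- Restricted estimates under π_T − π_C = 0.10: 0.1545 and 0.0545.
- s0 = √(0.1545×0.8455 + 0.0545×0.9455) = 0.4269
- s1 = √(0.09×0.91 + 0.08×0.92) = 0.3943
- n per arm = [(z₁₋α·s0 + z₀.₈₀·s1) / (Δ − (π_T − π_C))]²
- Alpha 0.025: [(1.960×0.4269 + 0.8416×0.3943) / 0.09]² = 168.57, so **169 per arm, 338 in total**. This matches the plan exactly.
- Alpha 0.05: [(1.645×0.4269 + 0.8416×0.3943) / 0.09]² = 132.0, so **132 per arm**. This does not match.

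The stated size therefore belongs to the non-inferiority direction at one-sided 0.025.

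**2. Probability of rejection in each direction.** This is an exact binomial enumeration of the Farrington-Manning z-test, with 169 per arm and true rates 9% vs 8%.

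| Hypotheses | Reject when | Probability |
|---|---|---|
| Non-inferiority pair | z ≤ −1.96 | 0.815 |
| Pair as printed | z ≥ +1.96 | 5.7e-7 |

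The claimed 80% power cannot refer to the printed alternative.

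**3. Illustration of the direction error.** Take 16/175 vs 14/175 events, close to the design rates (9.1% vs 8.0%). Then z = −2.74. The one-sided p-value is 0.003 for the non-inferiority pair and 1 − 0.003 = 0.997 for the printed pair. If failure to reject the printed null were read as success, a true 18% vs 8% with 175 per arm would pass about 97% of the time.

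**4. Effect of the confidence level** (non-inferiority direction, 175 per arm).

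| Quantity | One-sided 95% limit (alpha 0.05) | One-sided 97.5% limit (alpha 0.025) |
|---|---|---|
| False-pass rate at true 18% vs 8% | 5.1% | 2.4% |
| Upper limit for 21/175 vs 14/175 | 9.4%: passes | 10.6%: fails |

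The limits come from inverting the Farrington-Manning test. For 21/175 vs 14/175, z at the margin is −1.80 and one-sided p = 0.036, which lies between the two levels.

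**The case against.** The strongest reply is that the reversal is a drafting slip with little operational effect. The safety decision is a confidence-limit rule, stated twice in the right direction. The surrounding text says non-inferiority, and no section sets a p-value criterion for the safety endpoint. On that view the 6e-7 and 0.997 figures describe a test nobody plans to run. This largely stands: those figures prove the contradiction but do not predict the trial's result, and an analyst who follows the rule would test the right claim.

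It can also be said that the confidence-level mismatch is a separate defect. The printed hypotheses carry no alpha, so swapping the inequalities alone creates no new conflict. That is true, and the part that could change a verdict is the level, not the direction. The two are taken together because a complete correction should leave hypotheses, limit and alpha describing one test. It is fair to add that moving to a 97.5% limit makes the printed rule stricter, which should be acknowledged as a change.

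Finally, the inequalities were read from a PDF by a program. A reading fault is unlikely, since both lines would have to flip together and the efficacy pair came through correctly, but the source should be checked.

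**Conclusion.** The concern holds. The hypotheses in Section 12.1.2 are reversed relative to the success rule, the power statement and the sample size, all of which agree with one another on direction. Section 12.1.5 also contradicts itself on level: its one-sided 95% limit roughly doubles the false-pass rate at the margin (5.1% against 2.4%) compared with the 0.025 used for its own sample size.

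This should be fixed but is not fatal, because the confidence-limit rule already tests non-inferiority. The figures rest on the plan's own rates (8% and 9%), its margin and its named method. They also assume complete six-month data, on 169 or 175 subjects per arm as shown. The event counts in the illustrations are hypothetical.

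**What to change.** - **Section 12.1.2:** state H0: π_T ≥ π_C + Δ and HA: π_T < π_C + Δ, with Δ = 10 percentage points. Add that rejecting H0 at one-sided alpha 0.025 is the success criterion.
- **Section 12.1.5:** replace the one-sided 95% limit with an upper one-sided 97.5% limit, equal to the upper bound of the two-sided 95% interval. Name Farrington-Manning as the interval method so that the analysis matches the sample size.

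The cost is two lines and one phrase. The margin, the 169 per arm and trial conduct do not change. The printed limit in Section 12.1.5 becomes stricter, but only to the level that the synopsis, Section 12 and the sample size already state.
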